### **13.5 Appendix 5: Modified New York diagnostic criteria for ankylosing spondylitis**

Patients with axSpA are classified as having AS, based on the fulfillment of the 1984 modified New York diagnostic criteria ([van der Linden et al 1984](#)).

#### **Clinical criteria for ankylosing spondylitis**

- Low back pain and stiffness for more than 3 months that improves with exercise, but is not relieved by rest
- Limitation of motion of the lumbar spine in the sagittal and frontal planes
- Limitation of chest expansion relative to normal values correlated for age and sex

#### **Radiological criterion for ankylosing spondylitis**

- Sacroiliitis grade  $\geq 2$  bilaterally or grade 3–4 unilaterally

Definite AS if the radiological criterion is associated with at least one clinical criterion.

## 13.6 Appendix 6: Definition of sacroiliitis on imaging

### Sacroiliitis on magnetic resonance imaging

An MRI will be considered positive for sacroiliitis (active inflammatory lesions, “positive MRI”, MRI+) if the following characteristics are evident ([Sieper et al 2009](#)):

- The presence of definite subchondral bone marrow edema/osteitis highly suggestive of sacroiliitis is mandatory
- The presence of synovitis, capsulitis, or enthesitis only without concomitant subchondral bone marrow edema/osteitis is compatible with sacroiliitis but not sufficient for making a diagnosis of active sacroiliitis
- Amount of signal required: if there is one signal (lesion) only, this should be present on at least two slices. If there is more than one signal on a single slice, one slice may be enough

### Sacroiliitis on X-ray

Grading of radiographic sacroiliitis according to the New York diagnostic criteria ([Bennett and Burch 1968](#)):

- Grade 0: normal
- Grade 1: suspicious changes
- Grade 2: minimal abnormality (small localized areas with erosion or sclerosis, without alteration in the joint width)
- Grade 3: unequivocal abnormality - (moderate or advanced sacroiliitis with erosions, evidence of sclerosis, widening, narrowing, or partial ankylosis)
- Grade 4: severe abnormality (total ankylosis)

### **13.7 Appendix 7: Spinal pain numerical rating scale**

The spinal pain NRS is an 11-point scale to assess pain intensity in patients who are able to self-report. The patient is asked to answer 2 questions in order to make 2 pain ratings (point a number on NRS between 0 and 10), corresponding to the intensity of spinal pain experienced on an average during the previous week; the average of the 2 ratings is to be used to represent the patient's level of pain.

#### **Nocturnal back pain**

Based on your assessment, please indicate what is the amount of back pain at night that you experienced during the last week?

NRS scale 0 to 10, no pain to unbearable pain

#### **Total back pain**

Based on your assessment, please indicate what is the amount of back pain at any time that you experienced during the last week?

NRS scale 0 to 10, no pain to unbearable pain

### **13.8 Appendix 8: Bath ankylosing spondylitis disease activity index**

The BASDAI consists of a 0 through 10 scale (0 being no problem and 10 being the worst problem, captured as a continuous numerical rating scale), which is used to answer 6 questions (pertaining to the 5 major symptoms of AS):

1. How would you describe the overall level of fatigue/tiredness you have experienced?
2. How would you describe the overall level of AS neck, back or hip pain you have had?
3. How would you describe the overall level of pain/swelling in joints other than neck, back, hips you have had?
4. How would you describe the overall level of discomfort you have had from any areas tender to touch or pressure?
5. How would you describe the overall level of morning stiffness you have had from the time you wake up?
6. How long does your morning stiffness last from the time you wake up?

To give each symptom equal weighting, the mean (average) of the 2 scores relating to morning stiffness (questions 5 and 6) is taken. The mean of questions 5 and 6 is added to the scores from questions 1-4. The resulting 0 to 50 score is divided by 5 to give a final 0 – 10 BASDAI score. Scores of 4 or greater suggest suboptimal control of disease, and patients with scores of 4 or greater are usually good candidates for either a change in their medical therapy or for enrollment in clinical trials evaluating new drug therapies directed at AS. BASDAI is a quick and simple index (taking between 30 seconds and 2 minutes to complete).

## **13.9 Appendix 9: Guidelines for administering the questionnaires for patient reported outcomes**

### **Before trial start**

Study coordinators should familiarize themselves with the PRO questionnaires in the trial and identify any items where a patient's response might highlight issues of potential concern.

### **Before completion**

1. Patients should be provided with the correct questionnaire at the appropriate visits and in the appropriate language
2. Patients should have adequate space and time to complete the forms
3. Questionnaire should be administered before the clinical examination

### **During completion**

1. Administrator may clarify the questions but should not influence the response
2. Only one response for each question
3. Also see "Addressing Problems and Concerns"

### **After completion**

1. Check for completeness and not for content (However, any response which may directly impact or reflect the patient's medical condition (e.g. noting of depression) should be communicated by the study coordinator to the investigator)
2. Check for multiple responses that were made in error

### **Addressing problems and concerns**

Occasionally a patient may have concerns or questions about the questionnaires administered. Guidance related to some of the most common concerns and questions are given below.

#### **The patient does not want to complete the questionnaire(s)**

Tell the patient that completion of the questionnaire(s) is voluntary. The goal is to better understand the physical, mental and social health problems of patients. Emphasize that such information is as important as any other medical information and that the questionnaire(s) is simple to complete. Suggest that the questionnaire(s) may be different from anything the respondent has filled in the past. If the patient still declines, retrieve the questionnaires. Record the reason for the decline and thank the patient.

#### **The patient is too ill or weak to complete the questionnaire(s)**

In these instances, the coordinator may obtain patient responses by reading out loud each question, followed by the corresponding response categories, and entering the patient's response. Any person other than the designated study coordinator should provide no help to the patient. The coordinator should not influence patient responses. The study coordinator cannot translate the question into simpler language and has to be read verbatim.

### **The patient wants someone else to complete the questionnaire(s)**

In no case should the coordinator or anyone other than the patient provide responses to the questions. Unless specified in the study protocol, proxy data are not an acceptable substitute for patient self-report. Patients should be discouraged from asking a family member or friend for help in completing a questionnaire.

### **The patient does not want to finish completing the questionnaire(s)**

If non-completion is a result of the patient having trouble understanding particular items, ask the patient to explain the difficulty. Re-read the question for them verbatim but do not rephrase the question. If the respondent is still unable to complete the questionnaire, accept it as incomplete. Thank the patient.

### **The patient is concerned that someone will look at his/her responses**

Emphasize that all responses are to be kept confidential. Point out that their names do not appear anywhere on the questionnaire, so that their results will be linked with an ID number and not their name. Tell the patient that his/her answers will be pooled with other patients' answers and that they will be analyzed as a group rather than as individuals. Tell the patient that completed forms are not routinely shared with treating staff and that their responses will only be seen by you (to check for completeness) and by the investigator. Any response that may directly impact on or reflect their medical condition (e.g. noting of severe depression) will be communicated by the coordinator to the physician.

### **The patient asks the meaning of a question/item**

While completing the questionnaire, some patients might ask the meaning of specific items so that they can better understand and respond. If this happens, assist the patient by rereading the question for them verbatim. If the patient asks to interpret the meaning of an item, do not try to explain it, but suggest that he/she use his/her own interpretation of the question. Patients should answer the questions based on what they think the questions mean.

### **General information about all questionnaire(s)**

All questionnaires have to be completed by the patients in their local languages using an electronic device. The questionnaires should be completed by the patients in a quiet area free from disturbance, and before any visit assessments. Patients should receive no help from family members; if questions cannot be answered alone (due to problems with reading or understanding), then the doctor or nurse should read the questions and record the patient's responses without influencing their answers. The information provided is strictly confidential and will be treated as such. If a patient has missed a question or given more than one response per question, then this should be brought to patient. Incomplete questions should not be accepted without first encouraging the patient to complete unanswered questions.

The investigator must complete the patient/visit information on the electronic device and ensure that the center number, patient's number and initials are identical to the Case Record Form. As there are no source data for this questionnaire, the data queries will be restricted to patient/visit information.

### 13.10 Appendix 10: ASAS recommendations for collecting, analyzing and reporting NSAID intake

**Table 13-5 ASAD-NSAID equivalent score**

NSAID	Dose comparable to 150 mg diclofenac	Maximum dose used in AS	Consensus
Diclofenac	/	n=60* 150 (150-200)	150
Naproxen	n=57 1000 (1000-1000)	n=59 1000 (1000-1500)	n=47/50† 1000
Aceclofenac	n=15 200 (200-200)	n=14 200 (200-200)	n=29/29 200
Celecoxib	n=61 400 (300-400)	n=60 400 (400-400)	n=47/50 400
Etodolac	n=15 600 (400-800)	n=13 600 (600-600)	n=17/20 600
Etoricoxib	n=36 90 (90-90)	n=37 120 (90-120)	n=42/46 90
Flurbiprofen	n=13 200 (200-300)	n=13 300 (200-300)	n=15/18 200
Ibuprofen	n=54 2400 (1600-2400)	n=54 2400 (2400-2400)	n=39/45 2400
Indometacin	n=57 150 (100-150)	n=58 150 (150-200)	n=42/47 150
Ketoprofen	n=26 200 (200-200)	n=25 200 (200-300)	n=21/23 200
Meloxicam	n=58 15 (15-15)	n=55 15 (15-22.5)	n=42/48 15
Nimesulide	n=8 200 (200-200)	n=9 200 (200-200)	n=16/16 200
Phenylbutazone	n=28 400 (200-500)	n=28 400 (250-600)	n=25/28 400
Piroxicam	n=51 20 (20-20)	n=50 20 (20-40)	n=46/46 20
Tenoxicam	n=17 20 (20-20)	n=16 25 (20-40)	n=18/18 20

Source: [Dougados et al 2011](#)

Results of the survey evaluating the opinion of ASAS members about the comparable efficacy of each NSAID with 150 mg of diclofenac.

Values given are:

\*first row, n-number of ASAS members giving an answer to the question;

second row, median dose in mg (tertiles)

† first row, n=number of ASAS members who have voted in favour of such a dose/the total number of ASAS members who have voted; second row, agreed dose.

AS, ankylosing spondylitis; ASAS, Assessment of Spondyloarthritis International Society; NSAID, non-steroidal anti-inflammatory drug

LFT	Liver Function Test (raised serum transaminase and/or bilirubin levels)
MCII	Minimal Clinically Important Improvement
MedDRA	Medical Dictionary for Drug Regulatory Affairs
MMRM	Mixed Model Repeated Measures
MRI	Magnetic resonance imaging
NMQ	Novartis MedDRA Query

NSAID(s)	Nonsteroidal Anti-Inflammatory Drug(s)
NRS	Numerical Rating Scale
PASS	Patient Accepted Symptoms State
PD	Protocol deviation
PFS(s)	PreFilled Syringe(s)
PRO	Patient Reported Outcome
PT	Preferred Term
RAN	Randomized set
SAE	Serious Adverse Event
SAF-TP1	Safety Set for Treatment Period 1
SAF-TP2	Safety Set for Treatment Period 2
SAP	Statistical Analysis Plan
SMQ	Standardized MedDRA Queries
SOC	System Organ Class
SpA	SpondyloArthritis
TB	Tuberculosis
TBL	Total Bilirubin
TNF	Tumor Necrosis Factor
TNF α -IR	Tumor Necrosis Factor α Inadequate Responder
ULN	Upper Limit of Normal

1 Introduction

This document describes the planned statistical methods for all safety and efficacy analyses, which will be used in the phase IIb clinical trial CAIN457H3301.

The main purpose of this document is to provide summary of the statistical methodology that will be used for this clinical study; this includes a detailed description of data summaries. Analyses plan in this document refers to the related statistical analysis sections in clinical study report.

Data will be analyzed by Novartis using statistical software SAS version 9.4 according to the data analysis section 9 of the study protocol, which is available in Appendix 16.1.1 of the CSR (clinical study report). That statistical methodology is described below and any deviations from the protocol are documented. Additional detailed information regarding the analysis methodology is contained in the Appendix section 16.1.9 of CSR.

Please refer to the following document:

Clinical Protocol CAIN457H3301

1.1 Study design

This is a 24-week, randomized, double-blind, placebo-controlled, multicenter study to evaluate the efficacy and safety of secukinumab in controlling spinal pain in patients with axSpA. The study will consist of 2 treatment periods: a double-blind, placebo-controlled period from Baseline to Week 8 (i.e. Treatment Period 1) and a double-blind secukinumab treatment period from Week 8 to Week 24 (i.e. Treatment Period 2). At Baseline, patients will be randomized to either secukinumab 150 mg or placebo. At Week 8, patients will be re-randomized and re-assigned respectively to 1 of 5 treatment arms to receive either secukinumab 150 mg or secukinumab 300 mg.

The schematic of study design is given in Figure 1.1 below.

Planned number of patients and randomization

It is intended that a total of 352 patients (264 in secukinumab 150 mg group and 88 in the placebo group) will be recruited to compensate dropouts and protocol violators.

Patient eligibility criteria will be assessed during the Screening Period, which will occur for up to 10 weeks prior to randomization.

Treatment Period 1

At Baseline, patients whose eligibility is confirmed will be randomized to receive double-blind treatment with either secukinumab 150 mg or placebo (3:1) in Treatment Period 1 (Baseline to time of study drug administration at Week 8):

- **Group A:** secukinumab 150 mg (1 x 1.0 mL) s.c. administered at Baseline, Week 1, 2, 3 and 4
- **Group B:** placebo (1 x 1.0 mL) s.c. administered at Baseline, Week 1, 2, 3 and 4

Secukinumab 150 mg and matching placebo will be provided as 1.0 mL pre-filled syringes (PFSs).

On each treatment day during Treatment Period 1, one s.c. injection with either secukinumab 150 mg or placebo will be administered via PFSs.

Treatment Period 2

At Week 8, patients will enter Treatment Period 2 (Week 8 to Week 24). Patients randomized to Group A (secukinumab 150 mg) at Baseline will be assessed for the achievement of spinal pain NRS score and will be classified as responders (spinal pain NRS score < 4) or non-responders (spinal pain NRS score ≥ 4). Responders will be re-assigned to 1 treatment arm (Arm A1) to continue double-blind treatment with secukinumab 150 mg every 4 weeks from Week 8 to Week 24 (last dose administered at Week 20). Non-responders will be separately re-randomized to 1 of 2 arms to receive double-blind treatment with either secukinumab 150 mg or secukinumab 300 mg every 4 weeks starting at Week 8 up to Week 24 (last dose administered at Week 20).

Patients on secukinumab 150 mg who achieve spinal pain NRS score < 4 at Week 8 will be re-assigned to continue secukinumab 150 mg every 4 weeks (Arm A1)

- **Arm A1:** secukinumab 150 mg (1 x 1.0 mL) plus placebo (1 x 1.0 mL) administered at Week 8, 12, 16 and 20

Patients on secukinumab 150 mg who do not achieve spinal pain NRS score < 4 at Week 8 will be re-randomized to continue secukinumab 150 mg every 4 weeks (Arm A2) or to escalate to secukinumab 300 mg every 4 weeks (Arm A3):

[figure not shown]
- **Arm A2:** secukinumab 150 mg (1 x 1.0 mL) plus placebo (1 x 1.0 mL) administered at Week 8, 12, 16 and 20
- **Arm A3:** secukinumab 300 mg (2 x 1.0 mL) administered at Week 8, 12, 16, and 20

At Week 8, patients randomized to Group B (placebo) at Baseline will be re-randomized to either secukinumab 150 mg every 4 weeks (Arm B1) or secukinumab 300 mg every 4 weeks (Arm B2)

- **Arm B1:** secukinumab 150 mg (1 x 1.0 mL) plus placebo (1 x 1.0 mL) administered at Week 8, 12, 16 and 20
- **Arm B2:** secukinumab 300 mg (2 x 1.0 mL) administered at Week 8, 12, 16, and 20

During the study, patients will be required to self-administer secukinumab or placebo at all study visits and at home at Week 16.

On each treatment day during Treatment Period 2, two s.c. injections will be administered via PFSs either as 1 injection of secukinumab 150 mg and 1 injection of placebo, or 2 injections of secukinumab 150 mg. This is necessary to maintain the blind since secukinumab is supplied in 1.0 mL PFSs each containing 150 mg secukinumab, i.e. secukinumab 150 mg is supplied as 1 PFS and secukinumab 300 mg as 2 PFSs. Placebo to secukinumab will be supplied in 1.0 mL PFSs to match the active drug.

Figure 1-1 Study design

★ Patients will be stratified at baseline based on whether they are naïve to TNF α inhibitors or had an inadequate response (including intolerance) to TNF α inhibitors.

R+ = responder, i.e. patient with spinal pain NRS score < 4

R- = non-responder, i.e. patient with spinal pain NRS score \geq 4

axSpA=axial spondyloarthritis, BSL=baseline, PE=primary endpoint, SE=secondary endpoint, TNF α =tumor necrosis factor alpha, TNF α -IR=tumor necrosis factor α inadequate responder, W=week

Primary analysis time point

The primary analysis will be performed based on Week 8 assessment data. Average spinal pain NRS score will be considered as primary endpoint and will be analyzed for all applicable variables.

Interim analyses

No interim analysis is planned for this study.

The statistical analysis will be performed after all the patients have completed the study. Once all the data are complete and clean, the database will be locked and analyzed.

1.2 Study objectives and endpoints

Table 1.2-1 Objectives and related endpoints

Objective	Endpoint
Primary objective	
Superiority of secukinumab 150 mg compared to placebo in achieving a spinal pain score < 4 on a 0-10 NRS at Week 8.	Proportion of patients with a spinal pain NRS score < 4 at Week 8 in Group A compared to Group B.

Secondary objectives	
Superiority of secukinumab 150 mg compared to placebo in achieving a Bath Ankylosing Spondylitis Disease Activity Index (BASDAI) score < 4 at Week 8.	Proportion of patients with a BASDAI score < 4 at Week 8 in Group A compared to Group B.
Exploratory objectives	
Proportion of patients achieving a spinal pain score < 4 on a 0-10 NRS at Week 1, 2, 3 and 4 with secukinumab 150 mg compared to placebo.	Proportion of patients with a spinal pain NRS score < 4 in Group A compared to Group B at Week 1, 2, 3 and 4.
Proportion of patients in each treatment arm achieving a spinal pain score < 4 on a 0-10 NRS at Week 24.	Proportion of patients with a spinal pain NRS score < 4 in Arm A1, Arm A2 vs Arm A3, and Arm B1 vs Arm B2 at Week 24.
Proportion of patients in each treatment arm achieving BASDAI score < 4 at Week 24.	Proportion of patients achieving a BASDAI score < 4 in Arm A1, Arm A2 vs Arm A3, and Arm B1 vs Arm B2 at Week 24.
Proportion of patients in each of the treatment arms achieving Ankylosing Spondylitis Disease Activity Score (ASDAS) score < 2.1 at Week 8 and Week 24.	Proportion of patients with a ASDAS score < 2.1 in Group A compared to group B at Week 8 and in Arm A1, Arm A2 vs Arm A3, and Arm B1 vs Arm B2 at Week 8 and Week 24.
Proportion of patients in each treatment arm achieving ASDAS score < 1.3 at Week 8 and Week 24.	Proportion of patients with a ASDAS score < 1.3 in Group A compared to Group B at Week 8 and in Arm A1, Arm A2 vs Arm A3, and Arm B1 vs Arm B2 at Week 8 and Week 24.
Mean change from Baseline in functional assessment of chronic illness therapy-fatigue (FACIT-Fatigue [®]) score in patients on secukinumab 150 mg compared to placebo at Week 8.	FACIT-Fatigue [®] score in Group A compared to Group B at Week 8.
Mean change from Baseline in FACIT-Fatigue [®] score in each of treatment arm at Week 24.	FACIT-Fatigue [®] score in Arm A1, Arm A2 vs Arm A3, and Arm B1 vs Arm B2 at Week 24.
Proportion of patients in Arm A1 who have pain flares defined as NRS score > 6 at Week 12 or Week 24.	Proportion of patients who have pain flares, defined as NRS score > 6, in Arm A1 at Week 12 or Week 24.
Proportion of patients achieving a satisfactory Patient Acceptable Symptom State (PASS) at Week 1, 2, 3, 4 and 8 with secukinumab 150 mg compared to placebo.	Proportion of patients achieving a satisfactory PASS at Week 1, 2, 3, 4 and 8 in Group A compared to Group B.

Proportion of patients in each of treatment arm achieving a satisfactory PASS at Week 12, Week 20 and Week 24.	Proportion of patients achieving a satisfactory PASS at Week 12, Week 20 and Week 24 in Arm A1, Arm A2 vs Arm A3, and Arm B1 vs Arm B2.
Spinal pain NRS score according to previous exposure to tumor necrosis factor (TNF) inhibitors at Week 1, 2, 3, 4, 8, 12 and 24	Proportion of patients achieving a spinal pain score < 4 for TNF-naïve patients compared to TNF α -IR patients at Week 1, 2,3, 4, 8, 12 and Week 24
Proportion of patients who responded to secukinumab 150 mg at Week 8 (i.e. spinal pain score < 4 on a 0-10 NRS) maintaining a response at Week 24.	Proportion of patients with spinal pain score < 4 on a 0-10 NRS at Week 8 maintaining a spinal pain score < 4 at Week 24.
Proportion of patients achieving an improvement in ASAS health index with secukinumab 150 mg compared to placebo at Week 8.	Proportion of patients achieving an improvement in ASAS health index with secukinumab 150 mg compared to placebo at Week 8.
Proportion of patients achieving an improvement in ASAS health index in each treatment arm at Week 24.	Proportion of patients achieving an improvement in ASAS health index in each treatment arm at Week 24.
ASAS health index at Week 8 and Week 24.	Mean ASAS health index score in each treatment arm at Week 8 and Week 24
Change from baseline in total spinal pain NRS score at all time points.	Total spinal pain NRS score in each treatment arm at all time points.
Change from baseline in total BASDAI score at all time points.	Total BASDAI score in each treatment arm at all time points.
ASDAS-CRP at Week 8 and Week 24.	Mean ASDAS-CRP in each treatment arm at Week 8 and Week 24.
[REDACTED]	
[REDACTED]	
Safety and tolerability of secukinumab 150 mg and 300 mg over the study period.	Safety and tolerability, as measured by frequency and severity of adverse events and changes in laboratory values of interest for secukinumab 150 mg and placebo (Baseline to Week 8) and for secukinumab 150 mg and 300 mg (Week 8 to Week 24).

2 Statistical methods

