At the beginning of the study, the investigator/qualified study center staff will determine if self-administration is appropriate for the patient, e.g. manual dexterity, ability to follow the secukinumab PFS-IFU. If a patient requires a caregiver to administer study drug, the caregiver should be trained by the investigator/qualified study center staff. If a caregiver is not available at a particular visit or the patient is having problems with self-administration, the investigator/qualified study center staff may administer the study drug to the patient. However, all patients should be trained sufficiently and be comfortable with the study drug self-administration before the first home administration visit. Patients will be instructed to contact the investigator site staff in case of any issue during home administration of the study treatment.

Records of study drug kits assigned to the patient during the study must be documented.

At each visit, all study assessments, including the completion of PROs, should be completed prior to self-injection of the study drug.

Prior to and following self-administration at home, patients should contact the investigator/site staff in case they are experiencing any AEs, SAEs, or have any concerns.

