2.1.1 General definitions

Study treatment: Study treatment refers to:

Secukinumab 150 mg provided in 1 ml PFS or secukinumab placebo provided in 1 ml PFS.

Study treatment start and end date: Study treatment start date is defined as the first date, when a non-zero dose of study drug is administered and recorded on the Drug Administration Record (DAR) CRF page. Similarly, study drug end date is defined as the last date, when a non-zero dose of study drug is administered and recorded on the DAR CRF page of the core study.

Study day: Study day will be calculated as (event date – study drug start date + 1 day) for events that occurred on or after study drug start date (e.g., visit, lab samples, AEs). For events prior to study drug start date (e.g., time of diagnosis), study day will be negative and calculated as (event date – study drug start date). Note that study drug start date is study day 1 and the day before study drug start date is study day -1 (i.e. no study day 0).

Due to the study drug dosing schedule, one month will be considered as 28 days. However, for “time since event” data (e.g., medical history), one month will be considered as 365.25/12 days for events that occurred prior to study Day 1. Time from events prior to the start of study drug, e.g., time since diagnosis, is calculated as the difference between the start date of study drug and the date of prior event.

Note that, the first dose day is Day 1, and the day before the first dose day is counted as Day - 1 (not Day 0).

Baseline and post baseline: In general, a *baseline* value refers to the last measurement made prior to administration of the first dose of study treatment. A post-baseline value refers to a measurement taken after the first dose of study treatment.

Treatment Period: There are 2 treatment periods for this study defined as:

Treatment Period 1 is defined as an 8-week placebo-controlled, double-blind treatment period starting from baseline till Week 8. Assessments of Week 8 are included in TP1 whereas administration of study drug at week 8 will be a part of TP2. Week 8 is the last visit of TP1 for all assessments except drug intake.

Treatment Period 2 is a 16 week double-blinded, active treatment period starting from Week 8 till Week 24 for administration of study drug. Week 8 assessments are considered as the baseline values for assessments during TP2.

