- Proportion of patients in each treatment group with response in spinal pain score < 4 at Week 24.
- Proportion of patients in each treatment group with response in BASDAI score < 4 at Week 24.
- Proportion of patients in each treatment group with response in ASDAS score < 2.1 at Week 8 and Week 24.
- Proportion of patients in each treatment group with response in ASDAS score < 1.3 at Week 8 and Week 24.
- Proportion of patients in Arm 1 with spinal pain score > 6 at Week 12 or Week 24.
- Proportion of patients achieving a spinal pain score < 4 for TNF-naïve patients compared to TNF α -inadequate responder (TNF α -IR) patients at Week 8 and Week 24.
- Proportion of patients with response in spinal pain score < 4 to secukinumab 150 mg at Week 8 maintaining a response at Week 24. Only descriptive statistics will be presented for this endpoint.

The statistical significance of the above endpoints between groups will be analyzed by 95% CI of proportion. P-value will be added if there are enough number of patients available. The following continuous exploratory endpoints will also be summarized descriptively with number of patients (n), minimum, mean, standard deviation, median and maximum.

- Change from baseline in spinal pain score according to previous exposure to tumor necrosis factor (TNF) blockers at Week 1, 2, 3, 4, 8, 12 and 24.
- Change from baseline in total spinal pain score at all time points by each treatment group for each treatment period.
- Change from baseline in total BASDAI score at all time points by each treatment group for each treatment period.
- Change from baseline in ASDAS-CRP at Week 8 and Week 24.

If for a significant number of patients, the assignment to responder and / or non-responder status is incorrect, then a risk analysis may be performed.

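### Two exploratory ASDAS endpoints compare Arms A2 with A3 and B1 with B2 at Week 8, before the re-assigned treatment has started, so any difference within a pair at that visit is chance.

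*SAP*

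**What the plan says.** The ASDAS rows of Protocol Table 2-1 and SAP Table 1.2-1 (one row for the 2.1 cut-off, one for 1.3) name two comparisons. The first is Group A against Group B at Week 8. The second is by arm: "in Arm A1, Arm A2 vs Arm A3, and Arm B1 vs Arm B2 at Week 8 and Week 24".

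The arms do not exist before Week 8. SAP 1.1 says of Group A: "Patients on secukinumab 150 mg who do not achieve spinal pain NRS score < 4 at Week 8 will be re-randomized". Group B is re-randomised at the same visit to B1 or B2.

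On the order of events at a visit, Protocol 5.5.4 states that "all study assessments, including the completion of PROs, should be completed prior to self-injection of the study drug". SAP 2.1.1 draws the same line between the periods: "Assessments of Week 8 are included in TP1 whereas administration of study drug at week 8 will be a part of TP2". It adds: "Week 8 assessments are considered as the baseline values for assessments during TP2".

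SAP 2.1 presents Period 1 efficacy by Groups A and B, and Period 2 efficacy by the five arms.

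SAP 2.13 lists both ASDAS responses at Week 8 and Week 24 for each treatment group. For the endpoints in that list it says: "The statistical significance of the above endpoints between groups will be analyzed by 95% CI of proportion". A p-value is to be added if there are enough patients. Only the maintained-response endpoint is marked as descriptive only.

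**The concern.** A Week 8 contrast of A2 with A3, or of B1 with B2, sets one freshly randomised arm against another before the treatment that separates them has been given. It is a baseline comparison listed as an efficacy endpoint.

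Comparing 300 mg with 150 mg from Week 8 to Week 24 is a stated purpose of the study (Protocol 1.2). A chance imbalance at Week 8, shown with an interval and perhaps a p-value under a dose-comparison title, could be misread as evidence on that question. The listing also conflicts with SAP 2.1 and 2.1.1 taken together: Week 8 assessments are Period 1 data, and Period 1 data are presented by two groups, not five arms.

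**Working it through.** **1. Timing, from the documents.**

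| Pair | Formed | Assigned treatment up to the Week 8 assessment | Assigned from the Week 8 dose |
|---|---|---|---|
| A2 / A3 | Week 8, Group A non-responders | 150 mg / 150 mg | 150 mg / 300 mg |
| B1 / B2 | Week 8, Group B | placebo / placebo | 150 mg / 300 mg |

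Within each pair the assigned history is identical when ASDAS is measured, so the true dose effect at Week 8 is zero by design.

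**2. Comparison with the other rows.** In SAP Table 1.2-1, every other row that sets one arm against another does so after Week 8: spinal pain, BASDAI and FACIT-Fatigue at Week 24, and PASS at Weeks 12, 20 and 24. The two ASDAS rows are the exceptions.

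**3. The plan's sample size, used here only to size the arms.** The inputs in Protocol 9.8 and SAP 3 are 23.5% and 43.6% response, 3:1 allocation, two-sided 5% and 90% power. The pooled two-proportion formula with continuity correction gives 83 + 249 = 332, the stated figure. Planned recruitment is 264 + 88 = 352.

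**4. Expected arm sizes.** The documents give no re-randomisation ratio, so 1:1 is assumed.
- Group A non-responders: 264 × (1 − 0.436) = 148.9, or about 74 each in A2 and A3.
- Group B: 88 / 2 = 44 each in B1 and B2.

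**5. Size of a chance difference.** With no true difference and a proportion p at target in both arms of size m, 95% of differences lie within ±1.96 × √(2p(1 − p)/m). The documents give no ASDAS response rates, so a range is shown.

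| Assumed p | A2 vs A3 (m = 74) | B1 vs B2 (m = 44) |
|---|---|---|
| 5% | ±7.0 points | ±9.1 points |
| 10% | ±9.7 | ±12.5 |
| 20% | ±12.9 | ±16.7 |
| 30% | ±14.8 | ±19.1 |
| 40% | ±15.8 | ±20.5 |

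**6. False positives, if all four contrasts are tested at 5%.** There are 2 pairs × 2 cut-offs = 4 contrasts with a true null.
- All independent: 1 − 0.95⁴ = 18.5%.
- The two cut-offs fully correlated within a pair: 1 − 0.95² = 9.75%.
- Simulation with the cut-offs nested in the same patients (400,000 runs, pooled z test, 74 and 44 per arm): 17.6%, 18.5% and 18.1% when 5% and 20%, 10% and 30%, or 15% and 40% of patients are below 1.3 and 2.1 respectively. Single-test rates were 4.8% to 5.9%.

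So about 18% is the realistic figure. The 9.75% bound would require the two cut-offs to classify essentially the same patients.

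**The case against.** The best defence is that the analysis rules already settle the matter. SAP 2.1.1 puts Week 8 assessments in Period 1, SAP 2.1 presents Period 1 by Groups A and B, and SAP 2.13 speaks only of each treatment group without naming A2 against A3 at Week 8. Read together, Week 8 would mean A against B, and Week 24 the five arms. Protocol 3.5 also calls the work on the re-randomised arms descriptive, and Protocol 9.6 makes tests on exploratory endpoints optional.

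This shows how the conflict should be resolved, but it does not remove it. Both tables attach Week 8 to the arm comparison in so many words, right after a separate Group A against Group B comparison at Week 8. SAP 2.13 then places ASDAS at Week 8 among the endpoints assessed for significance between groups.

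Several stronger readings are tempting but not supported:
- *No patient has yet had the treatment of the arm.* A1 and A2 patients have had 150 mg since Baseline. What has not started is the re-assigned Period 2 treatment.
- *Arm A1 at Week 8 is a circular comparison.* A1 is selected on that day's pain score, but both tables list it alone. It is in no planned contrast.
- *The Week 24 contrast is biased without Week 8 adjustment.* It is a randomised comparison. Adjustment would gain precision, not remove bias.
- *The plan commits to four tests.* It plans intervals and makes p-values conditional on numbers, so the 18% applies only if all four are tested.
- *Every Week 8 ASDAS value is certain to be pre-dose.* Protocol 5.5.4 says should, and the pre-dose condition under SAP Table 2-1 is written for the primary endpoint only. A stray post-dose value up to Day 71 could be mapped to Week 8. That is a gap in the visit windows, not a reason for the comparison.

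**Conclusion.** The point holds as a defect in two exploratory endpoints. The Week 8 contrasts of A2 with A3 and B1 with B2 have no dose effect to detect, and they contradict the plan's own allocation of Week 8 data to Period 1. The documents' timing rules are enough to show this; no numerical assumption is needed.

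The size of the risk does rest on assumptions: 1:1 re-randomisation, the planned 352 patients, the assumed 43.6% response and an unstated ASDAS response rate. A reader might infer that the trial's main conclusions are exposed. They are not: both endpoints lie outside the confirmatory hierarchy of spinal pain followed by BASDAI. The consequence is limited to how the Period 2 dose comparison could be misread.

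**What to change.** - **Protocol Table 2-1 and SAP Table 1.2-1:** in the two ASDAS rows, limit the arm comparisons to Week 24 and keep Group A against Group B as the only Week 8 comparison.
- **SAP 2.13:** state that Week 8 ASDAS by arm is shown only to describe the Period 2 baseline, with no between-arm interval or p-value.
- **Week 24:** where an arm contrast is tested, adjust for the Week 8 ASDAS value. This is for precision, not to correct a bias.

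The cost is wording in two rows of each table and in SAP 2.13, plus one added model specification for the Week 24 contrasts. No new data are needed, since Week 8 ASDAS is already collected, and four comparisons drop out of the outputs. The protocol table can be changed only by written amendment (Protocol 11.1). If the correction is made in the SAP alone, it should be recorded in SAP section 4, which now lists no changes.
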